4.4 Sample size calculation

The sample size calculation of is based on three large randomised clinical trials which were published in high impact journals in 2014. From the DISCOVER, ESTABLISH and SOLO trials, information was gathered on cellulitis clinical cure rates as assessed by investigators after therapy:

DISCOVER²¹ (dalbavancin vs vancomycin-linezolid): (information from supplementary data)

- Clinical status evaluation at the end of therapy (day 14) of cellulitis patients:
 - o Cured: 297/324 and 276/301

ESTABLISH²⁷ (tedizolid vs linezolid): (information received from authors via e-mail)

- Investigator assessed response at post-therapy evaluation (7-14 days after end of therapy) of cellulitis patients:
 - o Cured: 265/301 and 263/307

SOLO²⁸ (oritavancin vs vancomycin): (information received from authors via e-mail)

- Investigator assessed clinical cure rates at the post-therapy evaluation (7-10 days after end of therapy) of cellulitis patients:
 - o Cured: 294/387 and 315/400

Total cure rates:

- $$(297+276+265+263+294+315) / (324+301+301+307+387+400) = 1710 / 2020 = 84,65\% \text{ cure rate}$$

A two-group large-sample normal approximation test of proportions with a one-sided 0.050 significance level will have 80% power to reject the null-hypothesis, assuming a success rate

of 85% and considering a difference of 10% between the two groups as equivalence limit, if the sample size of each group is 158. This gives a total sample size of 316 patients.

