7. METHODS

7.1 Study endpoints

7.1.1 Main study endpoint

The primary endpoint is resolution of cellulitis at 14-15 days, defined as disappearance of warmth and tenderness at the site of infection, with substantial improvement in erythema and edema, and without recurrence by day 28-29, defined as the need of additional antibiotic therapy for cellulitis.

This endpoint is in accordance with the study by Hepburn et al¹², and assumes that erythema and edema take longer to resolve than warmth and tenderness as seen in clinical practice.

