7.3.2 Cellulitis severity score

The severity of cellulitis will be graded at day 0, 2-3, 5-6, 14-15 and 28-29 using a clinical scoring sheet, in which the investigators assign an assessment (none, mild, moderate, or severe) to each of the following parameters: erythema, warmth, tenderness, edema,

ulceration, drainage, and fluctuance. Grading of each will be standardized among investigators at the beginning of the study by simultaneous readings. The grading designations none through severe are converted into a numerical value of 0 to 3 and these numbers were added to create a physician composite score for purposes of analysis (maximum score 21). This scoring system is the same as used in the most recent therapy duration study.¹² This will allow for measuring of objective (investigator-evaluated) improvement.

Two investigators (the PhD student and the trial nurse) will be responsible for data collection throughout the study. To minimize inter-observer variation and to promote data quality, initial patient assessment will be performed simultaneously by both investigators, and later independently and scores compared/evaluated. When five patients have been assessed independently, resulting in identical scores from both investigators, the investigators will start assessing patients on their own. After 100 patients have been assessed by a single investigator, the investigators will again assess five patients together, to compare scoring and thus improve data quality. During the course of the trial it will be evaluated if additional investigators need to be recruited, due to possible heavy workload and time spent on traveling between sites. Additional investigators will be trained by the PhD student in similar fashion as the trial nurse, with simultaneous and subsequent independent scoring as described above.

Patient self assessment scores will be performed at day 0, 2-3, 5-6, 14-15, 28-29 and 90 by visual Analog Scales (VAS) scores (rated 0-10) in order to determine the amount of pain and swelling patients experience accounting for subjective (patient-evaluated) improvement.

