9.2 Baseline characteristics

Statistical analysis will be based on the intention-to-treat principle. Baseline assessments and outcome parameters will be summarized using simple descriptive statistics.

Continuous variables will be summarized with standard descriptive statistics (e.g. mean, median, interquartile ranges, etc). Categorical variables will be summarized with frequencies and percentages. Ninety-five percent confidence intervals will be provided for descriptive statistics, as warranted.

Characteristic	6-day group	12-day group
Age (yr)		
Male sex (%)		
Ethnicity/race (white/black/asian/other)		
BMI (kg/m ²)		
No. of days of symptoms before presentation (days)		
Antibiotic treatment preceding presentation (%)		
Risk factors:		
- diabetes mellitus (%)		
- peripheral arterial disease (%)		
- lymphoedema (%)		
- non-diabetic ulcer (%)		
- venous insufficiency (%)		
- eczema / dermatitis (%)		
- trauma (%)		
- immunosuppression (%)		
- tattoos (%)		
- burns (%)		
- tinea pedis (%)		
- none (%)		
Cellulitis lesion surface area at presentation (cm ²)		
Axillary or inguinal lymphadenopathy (%)		
Resident at health care centre (%)		
Previous episode(s) of cellulitis (%)		
Smoker (%)		
Temperature at presentation (°C)		
Leukocyte count (x10 ⁹ /l)		
C-reactive protein (mg/l)		
Initial cellulitis severity score (score)		
Total % of positive cultures (%)		
- Streptococcus pyogenes (%)		
- Staphylococcus aureus (%)		
- MRSA (%)		
- Other Gram+ (%)		
- Gram- (%)		
Duration of hospital stay (days)		

Table 2. Baseline characteristics to be collected

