9.3 Primary study parameter(s)

For the primary outcome, the proportion of successful treatments will be calculated for the two groups, and the absolute risk difference (with one sided 95% confidence limit) will be estimated to evaluate the non-inferiority hypothesis. In a secondary analysis, the difference in proportion in the two groups will be adjusted for relevant baseline covariates, using a logistic regression analysis. The difference in proportion of successful treatments will be estimated at mean values for the covariates.

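### The deciding non-inferiority analysis is valid but unadjusted, and leaves unused the day 5-6 grades of the endpoint's own four signs: a modest, avoidable loss of efficiency

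*Combined protocol and SAP*

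**What the plan says.** Section 9.3 states that "the absolute risk difference (with one sided 95% confidence limit) will be estimated to evaluate the non-inferiority hypothesis", and the primary row of Table 3 names the same measure. Neither includes a covariate. Adjustment appears in three other places, and they do not agree:

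- Section 9.3 adds a secondary logistic analysis for relevant but unnamed baseline covariates, with the difference evaluated at the covariate means.
- The sensitivity rows of Table 3 give a Cochran-Mantel-Haenszel relative risk for the primary outcome.
- The Summary names both a chi-squared test and a covariate-adjusted Cochran-Mantel-Haenszel test as the means of evaluating non-inferiority.

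Section 7.3.2 says: "The severity of cellulitis will be graded at day 0, 2-3, 5-6, 14-15 and 28-29 using a clinical scoring sheet". Seven signs are each graded 0 to 3, including warmth, tenderness, erythema and edema. Section 7.2 places randomisation at day 5 and the start of study drug at day 6. The primary endpoint in section 7.1.1 requires "disappearance of warmth and tenderness at the site of infection, with substantial improvement in erythema and edema" at day 14-15, and no recurrence by day 28-29.

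Table 2 lists only the initial severity score. Table 3 does hypothesise, as a subgroup question, that severity affects cure, but does not say which day's score is meant. Severity is not a stratification factor (section 7.2).

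**The concern.** The day 5-6 grades are a pre-treatment measurement of signs that later decide the endpoint. A patient with marked warmth or tenderness at randomisation is plausibly less likely to be clear nine days later. If so, a crude difference leaves explainable variation in the standard error, and the confidence limit that decides the trial is wider than the collected data require.

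The initial score in Table 2 is a weaker substitute. Section 3.3 allows inclusion up to 72 hours after admission, so that score falls at different points of the illness. The day 5-6 score is taken at a common time, close to randomisation.

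The sample size in section 4.4 is set at the 80% target with no allowance for dropout, so a gain in precision at almost no cost is worth having.

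**Working it through.** **Inputs from section 4.4.** The test is planned "with a one-sided 0.050 significance level will have 80% power to reject the null-hypothesis". Cure is taken as 85% in both arms and the margin as 10 percentage points. The sample size is 158 per arm, 316 in total, with 1:1 allocation.

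**Step 1: reproduce the plan's figure.** With no covariate and a true difference of zero:

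n per arm = (1.6449 + 0.8416)² × (2 × 0.85 × 0.15) / 0.10² = 6.183 × 0.255 / 0.01 = 157.66, rounded up to 158.

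The stated number reproduces exactly, so the design takes no credit for any covariate.

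**Step 2: precision and power of the crude analysis.**

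SE = √(2 × 0.85 × 0.15 / 158) = 0.0402, or 4.02 points.

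Distance from estimate to one-sided limit = 1.645 × 4.02 = 6.61 points.

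Power = Φ(0.10 / 0.0402 − 1.645) = 80.1%.

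**Step 3: effect of adjustment.** The variance of a covariate-standardised (marginal) risk difference is approximately (1 − R²) times the crude variance, where R² is the share of outcome variance that the score explains. The documents give no R², so it is an assumption and a range is shown. Example at R² = 0.10: SE = 0.0402 × √0.90 = 0.0381, and power = Φ(0.10 / 0.0381 − 1.645) = 83.6%.

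| Assumed R² | Estimate to limit (points) | Power at 158 per arm | Total N for 80% |
|---|---|---|---|
| 0 | 6.61 | 80.1% | 316 |
| 0.02 | 6.54 | 80.8% | 310 |
| 0.05 | 6.44 | 81.8% | 300 |
| 0.10 | 6.27 | 83.6% | 284 |
| 0.20 | 5.91 | 87.2% | 254 |

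To put R² on a familiar scale, take a normally distributed score and 85% cure:

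| Odds ratio per SD | AUC | R² |
|---|---|---|
| 1.5 | 0.61 | 0.02 |
| 2 | 0.68 | 0.06 |
| 3 | 0.77 | 0.14 |
| 4 | 0.81 | 0.20 |

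**Step 4: check by simulation.** There were 6,000 trials per setting at 158 per arm, analysed by logistic standardisation with an influence-function standard error.

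| Odds ratio per SD | Crude power | Adjusted power |
|---|---|---|
| 1 (no association) | 79.4% | 79.3% |
| 1.5 | 80.0% | 80.6% |
| 2 | 79.5% | 81.4% |
| 3 | 79.3% | 83.8% |

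At a true 10-point deficit, type I error was 4.7% to 5.4% crude and 4.5% to 5.7% adjusted, with the two close in every setting. The Monte Carlo standard error is about √(0.05 × 0.95 / 6000) = 0.3 points. The simulation used a normal score and a correctly specified model. The real four-sign score is an integer from 0 to 12 (4 × 3), so the results are a guide to size and not a forecast.

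**The case against.** The strongest reply is that nothing is wrong with the crude analysis. Under randomisation it is unbiased for the quantity to which the margin refers, its limit matches the test used for the sample size, and it delivers its stated power. Chance imbalance in the day 5-6 score is already allowed for in the crude confidence limit. A simple primary estimate with adjustment as a secondary analysis is a legitimate choice. All of this stands.

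The gain also rests on an assumed association, and the documents suggest a weak one. Section 5.1 restricts randomisation to afebrile, improving patients without true positive blood cultures, which narrows the range of the score. The endpoint also requires no further antibiotics by day 28-29, which the score does not measure. Erythema and edema enter as a judgement of change, not as a level. So the score grades component signs of a composite; it is not a baseline value of the endpoint itself. This stands too, and points to the lower rows of assumed R².

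A third reply is that adjustment is already planned. This stands only in part. The plan does not exclude the day 5-6 score, but neither does it name it. Prediction at covariate means describes a patient with average covariates, not the population risk difference. A relative risk cannot be read against an absolute 10-point margin. The Summary and section 9.3 also differ on which analysis decides.

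A reader might infer that the trial is underpowered, that the crude result is biased, or that power near 90% is being given up. The documents support none of these. The planned 80% is met, the crude estimate is valid, and 89% power would need R² of about 0.25, an AUC above 0.81 for cure.

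**Conclusion.** The point holds as a matter of efficiency, not validity. The primary analysis leaves out pre-treatment grades of the endpoint's own component signs, although they are scheduled at the randomisation visit.

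Under assumed R² of 0.02 to 0.20, power would rise from 80.1% to between about 81% and 87%, and the limit would move 0.1 to 0.7 points closer to the estimate (6.61 − 6.54 and 6.61 − 5.91). The lower part of that range is the more plausible. The exact gain cannot be found from the documents. The case for change rests on the asymmetry: a likely small gain, against essentially no loss if the score proves uninformative.

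**What to change.** In section 9.3 and the primary row of Table 3, define the primary estimate as the marginal risk difference standardised over the trial sample. Obtain it from a logistic model with treatment and the day 5-6 sum of warmth, tenderness, erythema and edema. Take the one-sided 95% limit from a robust or bootstrap standard error, combine it across the multiple imputations of section 9.1, and read it against the same 10-point margin. In addition:

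- Keep the unadjusted difference as a sensitivity analysis.
- Replace prediction at covariate means with this standardisation.
- Add the day 5-6 score to Table 2.
- Bring the Summary into line, so that one analysis is named as deciding non-inferiority.

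No extra data are needed: section 3.3 already schedules the score at day 5-6. For weekend patients given a preliminary randomisation number, the score still precedes study drug and is graded blind, so it remains a valid covariate. The calculations here do not cover the first secondary endpoint, and the change is not proposed for it.

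The costs are reliance on a working model, some analysis code, the extra step of combining with multiple imputation, and a protocol amendment, possibly a substantial one under section 11.3. The amendment must be made before unblinding; a covariate chosen afterwards would not be credible.

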9.4 Secondary study parameter(s)

Differences in secondary outcome parameters will be reported as relative risk or mean difference (with 95% confidence interval), and p-values for statistical significance estimated with the Chi-square test, t-test or Mann-Whitney test, where appropriate. A Kaplan-Meier analysis will be performed to compare the time to relapse (defined as requiring additional antibiotics for cellulitis) between the two groups.

Variable/outcome	Hypothesis	Outcome measure	Methods of analysis
1. Primary			
Resolution without relapse	Intervention not inferior to control	Percent cured on day 14 without relapse by day 28 [binary]	Absolute risk difference
2. Secondary			
Resolution without relapse (per definition of protocol version 9.4, see paragraph 7.1.2, including both sensitivity analysis and per protocol analysis)	Intervention not inferior to control	Percent cured on day 14 without relapse by day 28 [binary]	Absolute risk difference (Per protocol analysis: χ^2 → Relative Risk)
Relapse by day 90	No difference	Percent with relapse [binary]	χ^2 → Relative Risk
Time to relapse	No difference	Relapse after cure [time to event]	Kaplan-Meier survival analysis
Objective speed of recovery	No difference	Cellulitis severity score [continuous]	Student's T-test or Mann-Whitney U test
Subjective speed of recovery	No difference	Visual analogue scales of pain and swelling [continuous]	Student's T-test or Mann-Whitney U test
Quality of life	No difference	SF-36 questionnaire score at day 0 and 90 compared to population, day 14 and 28 compared to day 5-6 [continuous]	Student's T-test or Mann-Whitney U test
Antibiotic usage	No difference	Total costs of antibiotic use [continuous]	Student's T-test or Mann-Whitney U test
Health care utilization	No difference	Total treatment associated costs, Health Care Utilization Questionnaire [continuous]	Student's T-test or Mann-Whitney U test
3. Subgroup analyses			
Cellulitis severity score on a continuous scale	Severity score affects rate of cure		Regression analysis, with interaction term for severity score
Diabetes mellitus vs no diabetes mellitus	Diabetes affects rate of cure		Regression analysis, with interaction term for (no) diabetes
4. Sensitivity analyses	Intervention not inferior to	All outcomes	

	control		
Per protocol analysis			Chi ² → Relative Risk
Primary outcome adjusted for baseline covariates			Cochran-Mantel-Haenszel → Relative Risk

Table 3. Analysis methods per outcome measures or variables

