5. TREATMENT OF SUBJECTS

5.1 Investigational product/treatment

After 5-6 days of treatment, patients who respond to therapy – defined as absence of fever (defined as temp $> 38.0^{\circ}\text{C}$) and clinical improvement since admission (either self-reported or investigator-assessed using the cellulitis severity score) – will be randomized in a blinded fashion with a 1:1 allocation ratio to receive 6 more days of (A) oral flucloxacillin or (B) oral placebo (both starting after day 6):

- (A) Regular treatment group: after the initial 6 days of flucloxacillin, another 6 days of oral flucloxacillin.
- (B) Intervention group: after the initial 6 days of flucloxacillin, 6 days of oral placebo.

Flucloxacillin treatment is administered as currently advised by the SWAB⁹: flucloxacillin intravenously 1000mg 4dd or orally 500mg 4dd, as a minimum. Some physicians will decide to dose differently, such as intravenously 1000mg 6dd, or orally 1000mg 4-6dd. This is allowed, but will be documented and can be taken into account during the analyses. No added benefit is to be expected from higher or more frequent dosing. Empirical treatment on admission can differ from flucloxacillin, provided it contains a beta-lactam antibiotic with anti-staphylococcal activity. Switch from intravenous medication to the oral route can be initiated before the 6th day of treatment at the discretion of the attending physician, but only if the patient has no fever (temp $> 38.0^{\circ}\text{C}$) and when the physician is convinced the cellulitis is improving. Patients who do not respond to treatment or whose blood cultures became positive (excluding contamination related positive blood cultures) will not be randomized and will be treated at the discretion of the attending physician. Their definitive diagnosis upon discharge, definitive antibiotic treatment and discharge date will be recorded.

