7.2 Randomisation, blinding and treatment allocation

Patients who respond to initial therapy will be randomized in a 1:1 ratio at day 5 by the commonly used online ALEA® randomisation software to one of two arms (starting at day 6):

(A) Standard course: after 6 days of flucloxacillin, another 6 days of oral flucloxacillin.

(B) Short course: after 6 days of flucloxacillin, 6 days of oral placebo.

The independent central randomisation service will create a computer generated random schedule in permuted blocks, stratified for diabetes mellitus (yes or no) and study site. The code will only be broken in case the DSMB advises to do so.

Hospital pharmacies are closed during the weekends, but there is a possibility that patients need to be evaluated for their day 5-6 timepoint somewhere during the period between Friday 16:00, and Monday 9:00, while they also need to receive their first dose of study medication in that period. For those patients, normal randomisation would be unfit because the study medication can't be delivered in time. For this minor group of patients, a different method of randomisation is used:

- Before Friday afternoon (ideally on the day 2-3 visit), the researchers will evaluate if the patient is likely to be randomised during the weekend period. If that is the case, the default checks in the eCRF are bypassed, and the patient is preliminarily randomised, thus assigning a randomisation number, and allowing the pharmacy to prepare the appropriate medication.
- Medication for these patients will be prepared by the AMC pharmacy, even if patients are admitted to other study sites. The researchers will collect the medication and store it in their workspace.
- Upon evaluation of the patient during the day 5-6 timepoint, the researchers will judge if the patient is able to be randomised according to the randomisation criteria.
 - o If the patient **can** be randomised, the medication will be given as if the patient was randomised as normal. Data entry will be done on the same day, and the built-in eCRF checks will automatically be performed during the night, confirming the appropriate randomisation.

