7.3.4 Health care associated costs

Patient information on antibiotic use and health care utilization for cellulitis related complaints (e.g. outpatient services, inpatient admissions, other health care provider services, use of antibiotics and other medication, assist devices or materials) will be collected at certain intervals. This will be collected through Health Care Utilization Questionnaires and patient records at days 5-6, 28-29 and 90. Parallel to this analysis, the EQ-5D-3L questionnaire will be utilized to index the health state of the patients and to accentuate the cost utility analysis.

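### The severity score and the pain and swelling VAS are compared without adjusting for the day 5-6 value, which is recorded before the first study capsule and would give extra precision at no cost

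*Combined protocol and SAP*

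**What the plan says.** Table 3 in section 9.4 gives all five continuous secondary rows (objective and subjective speed of recovery, quality of life, antibiotic usage, health care utilisation) the same method: "Student's T-test or Mann-Whitney U test". Section 9.4 adds that differences will be "reported as relative risk or mean difference (with 95% confidence interval"). No covariate is named for any of these rows. Adjustment appears only for the primary endpoint, in section 9.3 and in the Table 3 sensitivity row "Primary outcome adjusted for baseline covariates".

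The timing is clear. Section 7.2: "Patients who respond to initial therapy will be randomized in a 1:1 ratio at day 5". Section 5.1 describes the two capsule regimens as "both starting after day 6". Section 7.3.2: "The severity of cellulitis will be graded at day 0, 2-3, 5-6, 14-15 and 28-29 using a clinical scoring sheet", and for the VAS, "Patient self assessment scores will be performed at day 0, 2-3, 5-6, 14-15, 28-29 and 90". The day 5-6 severity score and VAS are therefore pre-capsule values of the outcomes analysed later.

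Section 7.1.2 describes speed of recovery in terms of improvement. Neither that section nor Table 3 says whether a change or a follow-up value is tested, from which baseline, or at which visit.

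**The concern.** When an outcome is also measured before treatment, a comparison that ignores the earlier value leaves in the error term all the between-patient variation that this value could have explained. A change score removes some of it but subtracts the baseline with a fixed coefficient of 1, which is inefficient unless the correlation is high. Here the value closest to the start of study treatment, at day 5-6, is already scheduled for every randomised patient.

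At stake is the precision with which the secondary objective on speed of improvement is answered. Most of these rows carry a hypothesis of no difference, so the width of the confidence interval decides how informative a null result is.

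**Working it through.** **1. The plan's own figure.** The only sample size calculation (section 4.4) is for the binary primary endpoint: 85% success in both arms, margin 10 percentage points, one-sided 0.05, 80% power.

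n per arm = (1.645 + 0.842)² × 2 × 0.85 × 0.15 / 0.10² = 157.7, rounded up to 158, or 316 in total. This reproduces the stated figure. Nothing below changes it. No power or precision is stated for the continuous secondary outcomes.

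**2. Inputs for the comparison.** 158 per arm (section 4.4), taken as fully observed; 1:1 allocation (section 7.2); 95% confidence intervals (section 9.4), taken as two-sided 0.05. The correlation ρ between the day 5-6 value and the follow-up value is not in the documents. I assume 0.3, 0.5 and 0.7.

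**3. Formulas.** Variance of the arm difference, relative to a t-test on the follow-up value:

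- follow-up value: v = 1
- change score, equal SDs at both visits: v = 2(1 − ρ)
- ANCOVA on the day 5-6 value: v = 1 − ρ²

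The ratio of ANCOVA to change score is (1 − ρ²) / [2(1 − ρ)] = (1 + ρ)/2. Confidence interval width scales with √v. The difference detectable at 80% power, in SD units, is √(2v/158) × (1.960 + 0.842). The equivalent unadjusted size per arm is 158/v.

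**4. Results.**

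| | ρ = 0.3 | ρ = 0.5 | ρ = 0.7 |
|---|---|---|---|
| ANCOVA v | 0.91 | 0.75 | 0.51 |
| Variance reduction against follow-up t-test | 9% | 25% | 49% |
| Confidence interval narrower by | 4.6% | 13.4% | 28.6% |
| Detectable difference, follow-up t-test (SD) | 0.315 | 0.315 | 0.315 |
| Detectable difference, ANCOVA (SD) | 0.301 | 0.273 | 0.225 |
| Equivalent unadjusted n per arm | 174 | 211 | 310 |
| Change score v | 1.40 | 1.00 | 0.60 |
| Detectable difference, change score (SD) | 0.373 | 0.315 | 0.244 |
| Variance reduction of ANCOVA against change score | 35% | 25% | 15% |

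The two readings of the plan pull in opposite directions. Against follow-up values the gain grows with ρ; against change scores it shrinks. ANCOVA has the smaller variance in every column.

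**5. Is day 5-6 safely pre-treatment?** Yes. Under the weekend procedure in section 7.2 a number may be assigned earlier, but capsules are handed over only after the day 5-6 evaluation.

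**6. Quality of life.** The schedule (3.3) and section 7.3.3 place the SF-36 at day 0, 28-29 and 90; the EQ-5D has the same visits in 3.3. Table 3 sets day 0 and day 90 against a population reference and days 14 and 28 against day 5-6. No SF-36 is scheduled at day 5-6 or day 14, so the second contrast cannot be computed as written. Day 0 is the only scheduled pre-capsule value.

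**7. Costs and antibiotic use.** Section 7.3.4: "This will be collected through Health Care Utilization Questionnaires and patient records at days 5-6, 28-29 and 90". The first collection precedes the capsules, but the Table 3 outcomes are totals with no stated costing window. The day 5-6 amount is therefore either a component of the total or a covariate from an earlier period. The formulas in step 3 are not applied to it.

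**The case against.** The strongest case on the other side is that nothing here is wrong. Randomisation makes the planned tests valid without covariates, chance imbalance is already reflected in their confidence intervals, these are secondary outcomes with no claimed power, and the primary endpoint has its own adjusted analysis. All of that stands. It makes this a matter of efficiency, not validity.

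The size is also open. Only afebrile, improved patients are randomised, and scores may lie near zero by day 14-15 or 28-29; both could lower ρ. A day 28-29 visit held by telephone yields no severity score. The step 3 comparison is with t-tests. No general ordering holds against a Mann-Whitney test on skewed data, although that test does not deliver the mean difference that section 9.4 promises.

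A reader might go further, in ways the documents do not support:

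- *Every continuous row ignores baseline.* The quality-of-life row names a day 5-6 reference, and speed of recovery may be meant as a change score, which does use the baseline.
- *The gain is that of nearly doubling the sample.* That needs ρ = 0.7 and a test on follow-up values. If change is tested, the same ρ gives a 15% variance reduction, worth about 18% more patients (1/0.85 = 1.18).
- *The cost totals contain hospital days before randomisation that only add noise.* No costing window is stated, so this is possible but not established.
- *Patients enter with widely varying residual severity.* No SD is given.

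**Conclusion.** The point holds for the severity score and the VAS, as an avoidable loss of precision in secondary analyses. A pre-capsule value is collected, no covariate is planned, and in large samples with 1:1 allocation ANCOVA is at least as precise as a t-test on follow-up values or on change, whichever the authors intended. The size ranges from modest to substantial, as tabulated, and rests on an assumed ρ and, for the change-score comparison, equal SDs; the lower end is plausible in this population.

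For quality of life the point holds in a weaker form: day 0 falls in the acute illness and may correlate poorly with day 28-29 or 90. The more direct defect there is the mismatch between Table 3 and the schedule. For costs and antibiotic use the gain is not quantified. The planned tests are not biased, and neither the primary conclusion nor the sample size is touched.

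**What to change.** In section 9.4 and Table 3:

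- **Severity score** (day 14-15 and 28-29) and **VAS** (day 14-15, 28-29 and 90): replace the two-sample tests by linear regression with robust standard errors on arm, the day 5-6 value and the stratification factors, that is diabetes and, where numbers allow, site. Report the adjusted mean difference with its 95% confidence interval at each visit. This also settles which value and which visit are analysed.
- **SF-36 and EQ-5D** (day 28-29 and 90): use the same model with the day 0 value as covariate. Reconcile the Table 3 contrast of days 14 and 28 with day 5-6 against the schedule.
- **Costs and antibiotic use**: keep the total as the outcome, so that the stated objective is unchanged, and state the costing window. If it includes the period before randomisation, adjust for the amount up to day 5-6.

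The cost is a wording change to the analysis section, made before unblinding. Every value needed is already scheduled; no visit, questionnaire or patient is added.
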